This is a single site study at Wake Forest School of Medicine. Thirty two subjects in total (16 volunteers, 16 subjects with painful knee arthritis), will receive a constant iv infusion of oxytocin for 30 minutes with a total dose of 14 μ g (micrograms), and verbal pain on a 0-10 scale to a 5 minute heating of the lateral calf to 45°C - 47 °C will be recorded. We will enroll up to 38 subjects if needed to obtain complete data sets for 32 subjects. We will provide this stimulus using an FDA-approved, commercially available device (Medoc TSA II). This short period of infusion will not result in steady state, but will produce slowly changing effects needed to create the pharmacokinetic / pharmacodynamic (PK/PD) model. The temperature to be delivered during the 5 minute heating will be determined during the screening visit. The primary outcome measure (pain at the end of 5-min heating) will be obtained before infusion and then at 4 times at 15 min intervals during and after the 30 min infusion. Subjects will be randomized to begin the first 5-min outcome measure test 3 min before infusion, at the time the infusion is started, or 2 or 5 min after it has begun (n=8 per cohort, n=32 in total). This staggered time of testing will allow the measurement at 5 min to be obtained frequently during increasing and decreasing serum concentrations (Figure 1). A PK/PD model will be calculated based on targeted OXT concentrations.

RATIONALE FOR USE OF PAIN REPORT TO SUSTAINED HEAT

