A single study of 10 young women used the LC/MS assay for oxytocin to define its pharmacokinetics after intramuscular injection [1]. Our long term goal is to examine efficacy of oxytocin in outpatient clinic settings (where intravenous infusion is not practical) in older men and women after major orthopedic surgery. The dose and timing of intramuscular oxytocin injection in that setting will depend on pharmacodynamic studies in this series, but also on knowing the pharmacokinetics in this population.

Objective

Main objective

Determine the effect of oxytocin during and after a fixed rate intravenous infusion on reduction in pain to a sustained heat stimulus in order to generate a PK/PD model for peripheral analgesia.

Methods and Measures

METHODS:

Equal numbers of adult men and women will be recruited from 2 populations. Sixteen patients with advanced knee arthritis being seen in the Orthopedic Clinic in consultation for potential total knee arthroplasty will be recruited after their doctor visit if the decision is made not to perform surgery at this time. Sixteen healthy volunteers without pain or taking pain medication will also be studied. At least 1 day prior to study subjects will be trained to rate pain in response to heat applied to the lateral calf using a Peltier controlled thermode.

Subjects will return for study visit two in which an intravenous catheter will be inserted, in the forearm for drug infusion. Oxytocin (Pitocin®) will be administered through a constant iv infusion for 30 minutes with a total dose of 14 micrograms (mcg) and verbal pain on a 0-10 scale to a 5 minute heating of the lateral calf to 45°C- 47 °C will be recorded. We will provide this stimulus using an FDA-approved, commercially available device (Medoc TSA II). This short period of infusion will not result in steady state serum levels, but will produce changing levels and effects needed to create the pharmacokinetic / pharmacodynamic (PK/PD) model. The primary outcome measure (pain at the end of 5-min heating) will be obtained before infusion and then at 4 times at 15 min intervals during and after the 30 min infusion. Subjects will be randomized to begin the first 5-min outcome measure test 3 min before infusion, at the time the infusion is started, or 2 or 5 min after it has begun (n=8 per cohort, n=32 in total). We will abandon an individual participant's study and schedule another participant should we be unable to successfully place the intravenous catheter.

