3. Women who are pregnant (positive result for urine pregnancy test at screening visit), women who are currently nursing or lactating, women that have been pregnant within 2 years
4. Subjects with neuropathy, chronic pain (located in any extremity other than the knee(s) or any other body location that is being treated), diabetes mellitus, or taking benzodiazepines or pain medications on a daily basis.
5. Subjects with current or history of ventricular tachycardia, atrial fibrillation or prolonged QT interval.
6. Subjects with past or current history of hyponatremia or at risk for hyponatremia; anyone taking thiazide diuretics, loop diuretics, combination diuretics, lithium, carbamazepine, enalapril, Ramipril, celecoxib, temazepam, gliclazide, glimepiride, glibenclamide, glipizide, omeprazole, pantoprazole, desmopressin, SSRI's, MAOI, or the recreational drug ecstasy.
7. Subjects with a known latex allergy.
8. Subjects with a pain score rating of 1 or less during the initial training session to a 5 minute heating of 45°C- 47 °C to the lower calf.

Sample Size

We request permission to study up to 20 subjects with knee arthritis and 18 healthy volunteers so that we will have 32 evaluable subjects, respectively, with complete data at all time periods.

Interventions and Interactions

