Study Visit 1: The participant will report to the Pain Research Unit at Piedmont Plaza II or the Clinical Research Unit (CRU) of the Wake Forest CTSI at least 1 day prior to study visit 2. The participant will review and sign the Informed Consent, if not already obtained. After informed consent is adequately obtained, a detailed medical history will be obtained from the participant, female participants will provide a urine sample to determine pregnancy status. Vital signs to include blood pressure (BP), heart rate (HR), respiratory rate (Resp) and peripheral oxygen saturation (POX) will be measured and recorded along with height and weight. The research nurse will train the participants to estimate pain quantitatively using a 2 cm² Peltier controlled thermode (TSA®) applied to a forearm with 5 sec presentation of stimuli at 39, 41, 43, 45, 47, 49, and 50°C, using a 11 point numerical verbal scale (NRS) anchored at 0 for no pain and 10 for the worst pain imaginable. Typically, the participant is exposed to temperatures between 38° and 51° C using a random staircase method. After this training, we will ask them to report pain intensity on the 0-10 NRS scale every minute for 5 minutes upon exposure to a 4 cm² Peltier controlled thermode at 45°C. If the subject scores the thermal pain less than 1 or zero during the heating of 113 degrees, we will move the thermal probe and repeat the 5 minute heating with a 115 degree heating for 5 minutes. If the subjects scores this heating less than 1 or zero, we will move the probe to a different location and one more increase will be made to a 117 degree heating for 5 minutes. If the subject scores this heating 1 or less they will be excluded from the study and we will replace them with another subject.

We have found this training session significantly reduces anxiety and variability in pain and hypersensitivity ratings on subsequent study days. The duration of this visit will be approximately 2 hours.

Study Visit 2

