Treatment of Side Effects: Mean blood pressure elevations greater than 30% of baseline will be treated with labetalol 5-15 mg IV incrementally until BP elevation is less than 30% elevated. Reductions in mean BP > 30% of baseline will be treated with incremental ephedrine 5-20 mg, IV. Heart rate (HR) reductions or elevations > 30% of baseline will be treated with incremental glycopyrrolate 0.2 mg IV or propranolol 0.2 mg IV, respectively. Peripheral oxyhemoglobin desaturation (< 90) will be treated with supplemental oxygen, nasal cannula, face mask, or non-rebreathing mask depending upon the degree desaturation and the response to therapy.

RISKS

Risks include privacy of data from their medical history and the result of the pregnancy test. Risks of the intravenous catheter include pain on and after insertion and local bruising. Risks of oxytocin in the nonpregnant individual are allergic responses and, during rapid infusion, transient (<15 min) headache and facial flushing. Additionally the following events have been reported as associated with the administration of oxytocin in the laboring female population:

- Anaphylactic reaction
- Postpartum hemorrhage
- Cardiac arrhythmia
- Fatal afibrinogenemia
- Nausea
- Vomiting
- Premature ventricular contractions
- Pelvic hematoma
- Water intoxication
- Subarachnoid hemorrhage
- Hypertensive episode
- Uterine rupture

Additional precautions are used in the presence of specific anesthetic medications; we are not administering any of these medications during this research study. Risks from the heat testing are temporary pain during testing and a superficial burn should the device malfunction. Please note that these devices are used in many pain clinics routinely and have multiple fail-safe designs to avoid thermal burn. The subject can ask for testing to be stopped at any time and withdraw from the study if they are uncomfortable with the thermal heating.

Outcome Measure(s)

Primary Outcome Measure

Name: Pharmacodynamics of heat pain after oxytocin

Type: Primary

[figure not shown]
Time Frame: Before and during infusions of oxytocin lasting 30-105 min

Description: Pain at the end of 5 minutes of heating the skin to 45 – 47 degrees C will be determined before, during and after infusions in order to create a PD model and validate the PK/PD model.

Analytical Plan

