This is an unblinded study with primary measure of drug effect to reduce heat pain in order to generate and then validate a PK/PD model. In the first study, 4 cohorts will be studied. The use of 4 cohorts is dictated by the desire to obtain 4 samples in the first 10 minutes after the beginning and end of infusion using a measurement that requires approximately 5 minutes to obtain and cannot be repeated more often than every 5 minutes. Staggering the measurements in each cohort provides adequate resolution of the time course of drug effect despite the inability to obtain frequent measurements in individual subjects.

The figure to the right shows the pain scores in the pilot study. The average CV at each time point for the pain measurements in the pilot study is 1.26. Our desired precision is to reduce the CV to 0.5, which requires a study size of 24.1 subjects ($1.96 * 1.253 / 0.5)^2$. Six subjects per cohort does not quite reach an adequate number (24), and 7 subjects per cohort cannot be equally divided between men and women, so we propose 8 subjects per cohort (N= 32, 4 cohorts @ 8 subjects / cohort).

The second study will attempt to determine the accuracy of the PK/PD model developed in Experiment 2.A and the first part of experiment 2.B. The N is taken from experiment 2.A.

Human Subjects Protection

All studies in volunteers will be performed in the CRU or in the Pain research Unit, which includes monitoring and resuscitation equipment and trained nursing support staff, or in in-patient settings of the Wake Forest Baptist Medical Center. All studies will be approved by the IRB and written informed consent obtained. The Project Investigators have all performed similar studies in volunteers and patients. The purpose of the study and all risks will be discussed with each volunteer, and all questions will be answered prior to obtaining written informed consent. Risks to be discussed include discomfort with needle and catheter insertion. All data acquired will remain confidential with no reference to individuals in publications.

Subject Recruitment Methods

Healthy subjects will be recruited from our current database of volunteers BG05-468, word of mouth and Be Involved website; the advanced knee arthritis population will be recruited from the Orthopedic Clinic at the Davie Medical Center Campus.

The research nurses; [name] and [name], LPN will conduct the recruitment of study subjects.

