The principal investigator will be responsible for the overall monitoring of the data and safety of study participants. The principal investigator will be assisted by other members of the study staff.

Data and Safety Monitoring Plan

Security of data and safety for anticipated and unanticipated adverse events will be monitored. Vital signs will be recorded during and after oxytocin infusion and adverse events recorded. An ongoing analysis of more than mild anticipated adverse events will be made after completion of each subject. Should there be more than 30% more than mild anticipated adverse events in the first 7 subjects, the remainder will receive a reduced or no highest planned oxytocin infusion step. Serious adverse events (SAEs) will be managed initially with stabilization within the CTSI and then with hospital admission and treatment. The study investigators are anesthesiologists well experienced in acute resuscitation and

emergency resuscitation resources are readily available within the CRU of the CTSI. SAEs will be reported within 24 hr to the IRB and the study stopped until a full report and outcome are determined.

We have obtained a waiver for Investigative New Drug (IND) approval for this study from the FDA, but will report SAEs to the FDA within 7 days.

An outside expert in oxytocin pharmacology and acute drug effects, [name], Director, Obstetric Anesthesia Service, Wake Forest School of Medicine, will insure that the trial is conducted according to the approved protocol and will carry out the DSMP.

Volunteer Payment

Participants will be paid a total of \$300 according to the following payment schedule which we have used throughout the last 2 cycles of this grant's protocols. We believe that this payment schedule is fair and appropriate, paying for each procedure attempted and an additional payment for completion of the entire study.

Completion of study 1: \$25

Placement of IV: \$25

Completion of entire study: \$250

Volunteer must complete all of the above phases to receive this payment.

If the subject is excluded from the study during study visit 1 due to the lack of pain felt during the thermal testing they will be compensated \$25 for this visit.

Long-term Follow-up

Volunteers will be contacted daily within the following week and questioned about adverse events from the study.

Reporting of Unanticipated Problems, Adverse Events or Deviations

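### Does the complete-data target of 32 subjects discard usable pain scores and select the analysed set on pain?

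*Combined protocol and SAP*

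**What the plan says.** Two places set the target. General Study Design states: "We will enroll up to 38 subjects if needed to obtain complete data sets for 32 subjects". Sample Size states: "We request permission to study up to 20 subjects with knee arthritis and 18 healthy volunteers", and gives as the reason "so that we will have 32 evaluable subjects, respectively, with complete data at all time periods".

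Under Risks, the protocol states: "The subject can ask for testing to be stopped at any time and withdraw from the study if they are uncomfortable with the thermal heating". Pain at the end of the same 5-minute heating is the primary outcome.

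Replacement is described in only two situations, both before dosing. Methods and Measures abandons a participant's study and will "schedule another participant should we be unable to successfully place the intravenous catheter". Study Visit 1 replaces anyone who scores 1 or less at the hottest training temperature.

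The Analytical Plan covers the four cohorts, the timing and the sample size. On timing it says "Staggering the measurements in each cohort provides adequate resolution of the time course of drug effect". It does not define an analysis set, a missing-data method or a score for a heating that ends before 5 minutes.

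**The concern.** If evaluable means complete at every time, and only evaluable subjects enter the PK/PD fit, then a dosed subject who stops because the heat hurts is left out. Inclusion would then depend on the primary outcome, and the highest pain scores would be the likeliest to go. Scores that the subject had already given would also be lost.

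The schedule makes each score look valuable. Each measurement time after the start of infusion rests on one cohort of eight, so one extra score adds 1/8 = 12.5% to the information at that time. The design also has no need of complete series, because it builds the time course by pooling a few measurements per subject across cohorts. With no written rule, the analyst would choose how to handle stopped heatings in an unblinded study with the scores in view.

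**Working it through.** **The plan's own figure.** The Analytical Plan gives n = (1.96 × 1.253 / 0.5)² = 24.1, and this reproduces (24.13). At 32 subjects the same measure is 1.96 × 1.253 / √32 = 0.434, inside the stated target of 0.5. Complete data from 32 subjects therefore meet the stated precision without any partial records.

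**Spare places.** 38 − 32 = 6, and 6/38 = 15.8%. By population, with 16 needed in each: 4/20 = 20% in arthritis and 2/18 = 11.1% in healthy volunteers. These are ceilings on the number of dosed subjects replaced for stopping. A failed catheter or a low-pain exclusion at training may use some of the same places.

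**Scores at stake.** Each subject gives one score before infusion and four later, so 32 completers give 32 × 5 = 160. A subject who stops at one of the four later tests has already given 1 to 4 scores. Six such subjects hold 6 to 24 scores, which is 3.75% to 15% of 160.

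**Measurement times.** Starts at −3, 0, 2 and 5 min, plus 5 min of heating, repeated every 15 min, give 2, 17, 32, 47; 5, 20, 35, 50; 7, 22, 37, 52; and 10, 25, 40, 55 min. That is 16 distinct times with 8 subjects each.

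**Bias at the ceiling.** A simulation used a random-intercept model with one baseline and four later scores. None of its settings come from the documents, except that the stopping rate equals the 15.8% ceiling:
- baseline mean 3, SD 1 or 2, within-subject correlation 0.5, 0.7 or 0.9;
- true fall 0 or 1 point;
- a fixed pain tolerance, set so that 15.8% stop and withdraw.

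The error is the estimated minus the true mean fall in pain, in points on the 0-10 scale.

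| Handling | Stops only after infusion starts | Stops at any visit-2 heating |
|---|---|---|
| Complete data only | +0.01 to +0.09 | −0.10 to 0.00 |
| All scores kept, stopped heating missing | +0.05 to +0.21 | not run |
| Stopped heating right-censored at the tolerance | 0.00 to +0.02 | 0.00 to +0.03 (baselines of undosed stoppers kept) |
| Right-censored 1 point too low | +0.04 to +0.06 | not run |
| Right-censored, dosed subjects only | not applicable | −0.17 to −0.02 |

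**Against sampling error.** The mean fall is the baseline score minus the average of four later scores, so its standard error is SD × √[(1 − correlation) × (1 + 1/4) / 32].
- SD 1, correlation 0.9: √(0.1 × 1.25 / 32) = 0.06.
- SD 2, correlation 0.5: 2 × √(0.5 × 1.25 / 32) = 0.28.

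Setting by setting, the complete-data error is at most about 0.3 of a standard error when stops come after infusion starts, and about 0.7 in the worst setting otherwise. At a 5% stopping rate it is at most 0.03 and 0.04 points respectively.

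**Likelihood of stopping.** Study Design expects pain of about 1 or 2 out of 10 at 113 °F, below the mean of 3 assumed above. The temperature is raised only for subjects who score below 1. Subjects meet the 5-minute heating at visit 1, so those who cannot tolerate it can leave before dosing. Under Volunteer Payment, $250 of the $300 is for completing the study, with the condition "Volunteer must complete all of the above phases to receive this payment".

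**The case for a change.** The strongest case for a change is that the gap is real and cheap to close. Both sample-size statements count complete records, the one documented reason to stop is tied to the primary outcome, and a pharmacokineticist at another institution fits the model without a written rule for partial series. The simulated subjects with complete data also average 0.16 to 0.56 points less pain than all subjects, so the pain level, as distinct from its change, would describe a milder group. Visit 1 already has subjects "report pain intensity on the 0-10 NRS scale every minute for 5 minutes", so a last rating before a stop could be recorded at visit 2 in the same way.

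Much of this stands as a point of tidiness. One sentence saying that all scores from dosed subjects enter the fit, and a note of when and why a heating stopped, would do no harm provided that the stopped heating is not then simply treated as missing. It does not show that the plan would give a wrong result. The stated objective is the reduction in pain, for which the subject's own baseline removes most of the difference in level. The more elaborate remedy, censoring stopped heatings, clearly beats complete data only when the last rating sits at the tolerance and the baselines of undosed stoppers are kept. Recorded one point low, its error overlaps that of complete data. Restricted to dosed subjects, it does worse. Keeping partial scores with the stop set to missing also does worse. Statisticians could reasonably differ on the choice.

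The Appendix lists a data collection form that is not shown, so whether stop time and reason are already captured cannot be judged.

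**Conclusion.** The concern does not call for a change. The complete-data wording fixes how many subjects to enrol. That partial records will be discarded is an inference from the word evaluable, and the staggered pooled design points the other way. The missing detail is one that an analyst would ordinarily fill by using every available score.

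If the strict reading were applied, the effect would be small and of uncertain sign: −0.10 to +0.09 points when 15.8% of subjects stop because of pain, and within about ±0.04 points at 5%. The 15.8% requires every spare place to go to a dosed subject who stopped because of heat pain, which the expected pain level makes unlikely. The stated precision is met by the 32 complete subjects alone.

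The conclusion rests on stops being uncommon, on effect being judged against each subject's own baseline, and on the assumed normal random-intercept model. The documents give no stopping rate. If many dosed subjects did stop because of pain, the handling of those heatings would need to be reported with the results.

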We aim to create pharmacokinetic/pharmacodynamic (PK/PD) models for oxytocin action at peripheral sites and at central sites as they relate to sensory transmission and pain. This is the second of 4 studies to accomplish generation and validation of a PK/PD model for oxytocin in the periphery. Its goal is to generate a PK/PD model by obtaining pharmacodynamic measures (reduction in pain report to sustained heat) at frequent intervals during and after a fixed rate intravenous infusion of oxytocin. Serum concentrations will be changing throughout the study as will the degree of pharmacodynamic effect. It is the time relationship between the serum concentration simultaneous to the effect which allows the model to be constructed. The study design assumes that Study 3 will find the 90% maximum serum oxytocin concentration to produce analgesia to a sustained heat stimulus is 90 pg/ml and that distribution of oxytocin from serum to its site of action in the periphery is rapid (< 5 min), based on our completed preliminary pharmacokinetic study.

GENERAL STUDY DESIGN

We aim to create pharmacokinetic/pharmacodynamic (PK/PD) models for oxytocin action at peripheral sites and at central sites as they relate to sensory transmission and pain. This is the second of 4 studies to accomplish generation and validation of a PK/PD model for oxytocin in the periphery. Its goal

is to generate a PK/PD model by obtaining pharmacodynamic measures (reduction in pain report to sustained heat) at frequent intervals during and after a fixed rate intravenous infusion of oxytocin. Serum concentrations will be changing throughout the study as will the degree of pharmacodynamic effect. It is the time relationship between the serum concentration simultaneous to the effect which allows the model to be constructed. The study design assumes that Study 3 will find the 90% maximum serum oxytocin concentration to produce analgesia to a sustained heat stimulus is 90 pg/ml and that distribution of oxytocin from serum to its site of action in the periphery is rapid (< 5 min), based on our completed preliminary pharmacokinetic study.

GENERAL STUDY DESIGN

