Any unanticipated problems, serious and unexpected adverse events, deviations or protocol changes will be promptly reported by the principal investigator or designated member of the research team to the IRB and sponsor or appropriate government agency if appropriate.

Data Share Plan Stanford Pilot Data

Scope of Work: [name] at Stanford University will establish and direct a pharmacokinetic/dynamic (PK/PD) modeling to facilitate future modeling in a NIH grant to be funded late 2021/early 2022. The PK/PD modeling will generate a mathematical model of oxytocin uptake, distribution, and elimination following intravenous delivery in humans. The PK/PD Core will use these mathematical models to describe the relationship between concentration at the site of effect and therapeutic response. The models will facilitate dosing regimens for future studies. The dose effect of intramuscular oxytocin will be modeled by the relationship noted on pupil diameter and heart rate variability and pupillary hippus measurements.

REFERENCES

1. De Groot, A.N., et al., *Bioavailability and pharmacokinetics of sublingual oxytocin in male volunteers*. J Pharm Pharmacol, 1995. **47**(7): p. 571-5.
2. Nielsen, E.I., et al., *Population Pharmacokinetic Analysis of Vaginally and Intravenously Administered Oxytocin in Postmenopausal Women*. J Clin Pharmacol, 2017. **57**(12): p. 1573-1581.

3. Nersesyan, Y., et al., *Oxytocin Modulates Nociception as an Agonist of Pain-Sensing TRPV1*. *Cell Rep*, 2017. **21**(6): p. 1681-1691.
4. Street, L.M., et al., *Capsaicin-induced pain and sensitisation in the postpartum period*. *Br J Anaesth*, 2019. **122**(1): p. 103-110.
5. Breton, J.D., et al., *Oxytocin-induced antinociception in the spinal cord is mediated by a subpopulation of glutamatergic neurons in laminae I-II which amplify GABAergic inhibition*. *Mol.Pain*, 2008. **4**(1): p. 19.
6. Jonas, K., et al., *Effects of intrapartum oxytocin administration and epidural analgesia on the concentration of plasma oxytocin and prolactin, in response to suckling during the second day postpartum*. *Breastfeed Med*, 2009. **4**(2): p. 71-82.
7. Quintana, D.S., et al., *Low-dose intranasal oxytocin delivered with Breath Powered device modulates pupil diameter and amygdala activity: a randomized controlled pupillometry and fMRI study*. *Neuropsychopharmacology*, 2019. **44**(2): p. 306-313.

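### The study-level adverse-event rule acts on a highest infusion step, but this study has one constant-rate infusion and no steps

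*Combined protocol and SAP*

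**What the plan says.** The rule is in the Data and Safety Monitoring Plan. Its trigger reads: "Should there be more than 30% more than mild anticipated adverse events in the first 7 subjects". Its action follows in the same sentence: "the remainder will receive a reduced or no highest planned oxytocin infusion step".

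The regimen is described elsewhere, each time as one infusion:

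- Goal of This Study: pain is measured "during and after a fixed rate intravenous infusion of oxytocin".
- General Study Design: subjects "will receive a constant iv infusion of oxytocin for 30 minutes with a total dose of 14" micrograms. The Methods and Study Design sections give the same duration and total.
- Study Design also states that every subject is dosed alike.
- Study Visit 2 describes one 30-minute pump infusion.

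The four randomized cohorts differ only in when heat testing starts relative to the infusion.

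**The concern.** A highest planned step presupposes at least two planned infusion levels, and this study has one. The rule's trigger can be evaluated, but its action cannot be carried out as written.

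This is the only numeric study-level rule for more-than-mild anticipated events. If it is met, staff and the IRB need to know at once what the next subject receives, and the protocol does not tell them. The outside expert "will insure that the trial is conducted according to the approved protocol and will carry out the DSMP", but on this point the approved text refers to something that does not exist in the study.

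A secondary gap is in the same sentence. The 30% most naturally means a proportion of subjects, but the text does not say whether it counts subjects or events.

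**Working it through.** The rule carries no derived figure to reproduce. The check is whether any text supplies a step, followed by simple arithmetic on the rule's reach.

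**1. Number of planned infusion levels.** General Study Design, Methods and Study Design all give 14 micrograms over 30 minutes at a constant rate: 14 / 30 = 0.467 micrograms/min. That is one rate, so no step is higher than another.

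**2. Text that might supply a step.**

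| Section | Wording that could suggest steps | Why it does not define one |
|---|---|---|
| Study Design | Pain relief is determined at each oxytocin level | The same sentence says the infusion is constant. General Study Design and Methods attribute the changing levels and effects to a short infusion that does not reach steady state |
| Outcome Measure(s) | Infusions in the plural, lasting 30 to 105 minutes | A range of durations, in an entry that also covers validating the model; no rates or steps are given |
| Analytical Plan | A second study to test the model's accuracy | A separate exercise, with no regimen stated |

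**3. Literal readings of the action.**

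- (a) No step exists, so nothing changes.
- (b) The only infusion counts as the highest step and is reduced. The size of the reduction is not stated.
- (c) The only infusion counts as the highest step and is omitted. The remaining subjects then receive no oxytocin, which in effect ends the study, although the plan does not say so.

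Readings (b) and (c) depart from the fixed total in General Study Design and from the identical dosing in Study Design. Neither section names an exception.

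**4. Where the trigger falls, counted by subject.** The condition is k/7 > 0.30.

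- 2/7 = 28.6%: not met.
- 3/7 = 42.9%: met.

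So three or more affected subjects out of seven would trigger the rule. Counting events could give a different answer, because one subject may have several.

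**5. Subjects governed by the undefined action.** This assumes the rule is applied once 7 subjects are complete.

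- Planned size: 32 − 7 = 25, and 25/32 = 78.1%.
- Enrolment ceiling (General Study Design): 38 − 7 = 31, and 31/38 = 81.6%.

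The second figure is an upper bound. Some of the 38 may never be infused, because subjects can be excluded at heat screening or dropped if the catheter cannot be placed.

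**The case against.** The strongest reply is that the intent is plain. The rule says the remainder will receive a reduced something or none of it, so it clearly means a change, and reading (a) is weak. A contingent safety rule also normally departs from the planned regimen once triggered, so a departure from the 14 micrograms is not a contradiction in itself. The protocol belongs to a series of related studies and has other wording that reaches beyond this one, so the phrase may have been carried over from a sister study. That would make it an editorial slip.

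Other safeguards also operate. "An ongoing analysis of more than mild anticipated adverse events will be made after completion of each subject". For serious events, "SAEs will be reported within 24 hr to the IRB and the study stopped until a full report and outcome are determined". Individual vital-sign, treatment and discharge rules apply under Safety and Monitoring. Under the reporting section, "deviations or protocol changes will be promptly reported by the principal investigator" or a designated member of the team.

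Much of this stands. Reading (a) is the least likely of the three. The conflict with the regimen sections is only that they name no exception. The safeguards do limit the harm. But a carried-over phrase would explain the mismatch without curing it. Even without reading (a), the choice between an unspecified reduction and no drug at all remains open, and no safeguard settles it.

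**Conclusion.** The concern holds. The study-level rule for more-than-mild anticipated events has an action with no referent in a single-rate design. This is wrong as written and should be fixed. The safeguards that still operate keep it from being graver.

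If triggered after the seventh subject, the gap affects 25 of 32 planned subjects (78%), and at most 31 of 38 (82%). Both figures are conditional on the trigger. The documents give no event rate, so no probability of triggering is claimed. The threshold of three in seven assumes the 30% counts subjects. The conclusion about the action does not depend on that assumption.

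**What to change.** Reconcile the Data and Safety Monitoring Plan with General Study Design, Methods and Study Design, so that the action refers to something the single-infusion design contains and the regimen sections acknowledge it. What the action should be is a clinical decision for the investigators and the IRB, and none is proposed here.

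In the same sentence, state that the 30% is the proportion of subjects with at least one such event, or state the other unit intended.

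Add that, if any subject's infusion is changed under the rule, the infusion actually given is that subject's input to the PK/PD model. This matters because General Study Design bases the model on targeted concentrations, and the visit procedures describe a catheter for infusion only. Entering the planned 14 micrograms for an altered subject would misstate that subject's exposure.

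The cost is one or two sentences in a protocol amendment. Sample size, visits and data collection do not change.
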